9.2.4 Data Collection

Data collection will occur at the site level in accordance with the process outlined in Figure 1. Data for case ascertainment of each outcome will be collected in an electronic case report form (eCRF). Since non-cases will be excluded from the study, vaccination information should be collected only on cases that have been confirmed by medical record review adjudication. Data on COVID-19 vaccination for the confirmed and probable cases will be collected in a separate eCRF, to allow for blinding of timing of the event relative to vaccination when collecting exposure information.

[The investigators should describe the data collection tools to be used].

Figure 1. Operational Steps to Identify Cases and Exposure Information for the SCRI, CCO, and Vaccinated Case-Coverage Designs

CCO = case-crossover; CRF = case report form; SCRI = self-controlled risk interval.

9.2.5 Variables

In this section, outcomes, exposures, covariates, and their operational definitions will be described. As general reference and for the opportunity to harmonise study methods, it is recommended that investigators review the output of the Safety Platform for Emergency vACcines (SPEAC) project, which is developing event definitions, code lists, lists of risk factors, and risk window definitions for many of the AESI. This information will be released on the Brighton Collaboration website in the coming year (<https://brightoncollaboration.us>).

9.2.5.1 Outcome Assessment

In this section, the operational definitions for identifying <<adverse event>> in electronic data should be described, with reference to code lists included in a separate protocol appendix.

[Outcome definitions for the proposed adverse events, including code lists, are currently being developed by another workgroup in this project and will be incorporated in this protocol when they become available.]

<<Adverse event>> will be identified in each participating hospital's discharge database or other electronic data bases using diagnosis codes, or a combination of diagnosis with

procedure or treatment codes in the inpatient, emergency department, or ambulatory speciality care settings. Additionally, electronic laboratory data could be used to identify events, if applicable to the outcome.

For recurrent events in the SCRI design, “washout periods” anchored on the outcome date will be used to identify incident events when multiple visits or codes for the same event occur during follow-up; any events with another event (in any care setting, including inpatient, emergency room, hospital outpatient, or primary care) within the washout period will be excluded. For recurrent events in the case-cross over and vaccinated case-coverage designs, only the first event observed during the study period will be included.

Case validation will be undertaken by clinical reviewers blinded to vaccination status and timing of the event relative to vaccination. Case status and date of outcome onset will be confirmed using medical records, physician questionnaire, or other official documentation (e.g., clinical case notes), depending on the data source. Case status will be determined based on Brighton Collaboration definitions where available [2]. SPEAC is developing a toolbox for case definitions that can be obtained on the Brighton Collaboration website or through the following e-mail address: [contact]. The comparative analysis will only include confirmed cases and the dates of onset assigned by the clinical reviewers.

9.2.5.2 Exposure Assessment in Cases

In this section, operational definitions for identifying exposure should be described, including type of vaccine codes.

Exposure status will be identified in confirmed and probable cases. For this study, an indicator for each dose of <<COVID-19 vaccine product>> and date of vaccination will need to be identified for all cases. In the SCRI design, if multiple doses of vaccine are given during the study period, each individual dose will be evaluated separately. To the extent feasible, in the case of multidose vaccines, exposure information should be captured following hospital discharge to avoid bias due to the outcome impacting the observation period for exposure. If collecting exposure information after hospital discharge is not possible, the impact of this potential bias could be explored in a sensitivity analysis using Farrington’s pseudolikelihood method for censored, perturbed, or curtailed postevent exposures [7].

In the primary analysis, exposure will be based on a specific COVID-19 vaccine product; a secondary analysis will be conducted stratified by vaccine groupings defined by technology, platform, or components (e.g., mRNA, adenovirus backbone, protein recombinant vaccines, adjuvant). If the concern for a particular outcome is related to a specific product (as per data existing at the time of full protocol development), the analysis for the particular outcome will only be conducted for the specific product, and a combined analysis of products will not be conducted.

Exposure information will be obtained from pharmacy dispensing records, general practice records, immunisation registers, vaccination cards, medical records, and/or other secondary data sources. The availability and feasibility of data sources to obtain vaccination information will likely vary by jurisdiction. Depending on the data source, vaccines may be identified via Anatomical Therapeutic Chemical codes, nationally used codes, local codes, or free text. If vaccination cards are used, and if feasible, a sample of vaccine records could be validated against other sources such as medical records or health care provider questionnaire to confirm the vaccine product and date of vaccination.

If the vaccine is administered in multiple doses, then each exposure code will be considered to be a separate instance of vaccination, provided that sufficient time has passed between the dates of the codes, based on the vaccine dosing schedule and taking into account the possibility that some persons may receive subsequent doses slightly earlier than indicated in the vaccine dosing schedule (for example: if the vaccine dosing schedule calls for two doses at least 28 days apart, then any code for vaccination that occurs fewer than 21 days after the first code would be excluded, under the assumption that any additional codes after the first code are duplicates of the same dose). If the vaccine is administered as a single dose, then only the first exposure code during the study period will be considered, which assumes that the remaining codes are errors.

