9.2.5.3 Risk and Control Windows

In this section, risk/exposure windows will be defined for <<adverse event>> in table format.

SCRI

If the SCRI is used, a risk window, in which person-time will be considered exposed, will be selected after vaccination to reflect the hypothesised period of increased risk of the outcome due to vaccination. By convention, the risk window will index on the date of vaccination, which will be time = 0. A postvaccination control window will be selected to estimate the baseline rate of the outcomes. The control window definition (length and timing relative to vaccination) will be the same across individuals and will balance the need to obtain adequate statistical power against the threats of bias due to loss to follow-up and time-varying confounding. A washout period following the risk window may be incorporated to avoid any carryover effects of the vaccine into the postvaccination unexposed person-time.

If multiple doses of vaccine are given during the study period, the risk and control windows of one dose must not overlap with the risk or control windows of a subsequent dose, based on the vaccine dosing schedule. Some possible approaches to define the control interval, depending on the length of the risk interval and spacing between doses of the vaccine, are provided below:

- If there is a short interval between doses of the vaccine and a long risk interval, it would be necessary to avoid overlap of the risk interval of one dose with the risk and/or control intervals of a subsequent dose; depending on the length of the risk interval and the spacing between doses, it may be necessary for the control interval to be positioned after the risk interval of the final dose. For example, suppose the vaccine is administered in two doses approximately 28 days apart, and the outcome of interest has a risk interval of 1 to 42 days. Conducting a dose-level analysis (i.e., considering each dose to be a separate observation), with a risk interval of 1 to 42 days following each dose could potentially lead to confounding of the first dose by receipt of the second dose, and vice versa. To address this, a person-level analysis could be conducted combining the risk intervals following each exposure, for example:
 - For persons who receive two doses, define the risk interval as 1 to 42 days after the first dose plus 1 to 42 days after the second dose. The control interval could then be defined as 43 to 127 days after the second dose.

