 - For persons who receive only one dose, define the risk and control intervals as 1 to 42 and 43 to 127 days after vaccination, respectively.
 - In the above scenarios, the control window could be placed even further in time from vaccination to incorporate a washout period between the risk and control intervals, as needed.
- If there is a short interval between doses of the vaccine but the risk interval is short, a dose-level analysis (treating each dose as a separate observation) could be conducted, but care must also be taken to ensure that the control interval does not overlap with the next dose. For example, suppose the vaccine is administered in two doses approximately 28 days apart, and the outcome of interest has a risk interval of 0 to 7 days. The control interval would need to end before 27 days after vaccination (e.g., 8-15 days) to ensure that there is no overlap of the control interval of the first dose with the risk interval of the second dose.

If the outcome affects the likelihood of a subsequent vaccination after the first dose, the impact of this potential bias could be explored in a sensitivity analysis using Farrington’s pseudolikelihood method for perturbed, censored, or curtailed observation periods for postevent exposures [7].

CCO Design

If the CCO design is used, an exposure window preceding the event will be selected to reflect the period during which exposure to COVID-19 vaccination is hypothesised to trigger the adverse event of interest. A single comparison window preceding the risk window will be selected to reflect the baseline prevalence of exposure; the comparison window should be selected independently of exposure status. Multiple comparison windows per case may also be considered but are not recommended because they may increase the potential for bias due to time-varying confounding and temporal trends in

exposure. By convention, the exposure window will index on the date of the adverse event, which will be time = 0. A washout period between the exposure and comparison windows can be implemented to avoid any carryover effects of the vaccine between the two windows.

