9.4 Study Size

Statistical power is driven by the number of confirmed cases and the ratio between the duration of the risk and control periods. In Table 3, we provide the estimated number of cases (i.e., vaccinated cases with an event in the risk or control interval) needed for a SCRI design to have 80% power under a range of assumed effect sizes and the proportion of the observation period in the risk interval (number of days in the risk interval/[number of days in the risk interval + number of days in the control interval]) [8].

Additionally, based on the range of assumed relative incidences, durations of the risk and control intervals, background rate, and assumed vaccine uptake, one could estimate the total population size of the catchment areas for the hospital sites needed to achieve the necessary sample sizes. Other approaches may be acceptable to estimate study size.

Table 3. Sample Size Needed to Achieve 80% Power for the Self-controlled Risk Interval Design

Proportion of the Observation Period in the Risk Interval	Relative Incidence	Sample Size (Number of Cases)
25%	1.5	230
25%	2	74
25%	2.5	41
25%	3	28
25%	3.5	21
33%	1.5	203
33%	2	68
33%	2.5	38
33%	3	27
33%	3.5	21
50%	1.5	194
50%	2	69
50%	2.5	41
50%	3	29
50%	3.5	23

[To be completed by the study investigator(s) based on assumptions regarding length of the risk and control intervals and effect estimate size at the time of the full protocol development.]

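### The first-code rule for dating a dose lets a pharmacy dispensing date displace the administration date, which generally biases a true risk toward the null

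*Protocol*

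**What the plan says.** Protocol section 9.2.5.2 sets the rule for repeated vaccination codes. A code counts as a separate dose if enough time separates it from the others, judged from the dosing schedule. The worked example takes two doses at least 28 days apart and says that "any code for vaccination that occurs fewer than 21 days after the first code would be excluded". The ground given is that such codes merely record one dose again. For a single-dose vaccine, "only the first exposure code during the study period will be considered, which assumes that the remaining codes are errors"; here there is no day limit.

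On sources, the same section says: "Exposure information will be obtained from pharmacy dispensing records, general practice records, immunisation registers, vaccination cards, medical records, and/or other secondary data sources". It adds that availability will differ between jurisdictions. It does not rank the sources and does not separate a dispensing date from an administration date.

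Section 9.2.5.3 states for the self-controlled risk interval (SCRI) design that "the risk window will index on the date of vaccination, which will be time = 0". One worked example there assumes that "the outcome of interest has a risk interval of 0 to 7 days" and offers days 8-15 as the control interval, directly after the risk interval.

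**The concern.** A dispensing date cannot fall after the administration of that dose but can fall before it. If a person has both records and the dates differ, a rule that keeps the earliest code always keeps the dispensing date and deletes the administration date as a duplicate or an error. The mistake is therefore systematic: the recorded time zero is too early and never too late.

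In the SCRI this moves true risk days out of the front of the risk window and, if the lag is long enough, into the control window. Both effects generally pull a real excess toward no effect. In a safety study that is the direction that hides harm.

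No other section corrects this:
- Section 9.3 requires sites to be able to identify the vaccination date but does not say which date counts.
- Validation of the vaccination date (9.2.5.2) is optional and tied to vaccination cards.
- Section 9.6.5 varies risk windows and event dates, not vaccination dates.
- Section 9.8 concedes that the validity of vaccination dates is unknown.
- Annex 5 accepts dispensing data (item 18) and asks only whether dates are captured exactly or partly imputed (item 25).
- Section 9.5 runs one common programme at all sites, so the rule would apply everywhere.

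**Working it through.** **Inputs from the protocol.** SCRI risk days 0-7 and control days 8-15 (8 days each, so 50% risk time); SCRI 1-42 and 43-127; case-crossover (CCO) exposure window 1-21 and comparison window 50-70 days before the event (all 9.2.5.3). Table 3 in 9.4 gives 29 cases for 80% power at relative incidence 3 and 50% risk time.

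**Assumptions.** True ratio 3, a value that Table 3 covers. Recorded date *L* days too early in a fraction *f* of vaccinees; neither is in the documents. Two-sided alpha 0.05, which the protocol does not state.

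**Table 3 first.** With risk share r and relative incidence ρ, let q = ρr/(ρr+1−r), A = 2[q ln ρ − ln(ρr+1−r)], B = (ln ρ)²q(1−q)/A. Then n = (1.960 + 0.842√B)²/A. For r = 0.5 and ρ = 3: q = 0.75, A = 0.2616, B = 0.865, n = 28.75, rounded up to 29. This matches the protocol.

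**Windows 0-7 and 8-15.** Count expected events by day, with baseline 1 and a rate of 3 on the eight days from true administration. Correctly dated people give 8×3 = 24 in the risk window and 8 in the control window. For L up to 8, each day of lag swaps one raised day for a baseline day in the risk window, and the reverse in the control window:

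expected ratio = (24 − 2Lf)/(8 + 2Lf)

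At L = 8 this is (24 − 16f)/(8 + 16f). Power at 29 cases uses q = ratio/(1+ratio) and Φ{[(q − 0.5)√29 − 1.96×0.5]/√(q(1−q))}. Cases needed use the Table 3 formula.

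| Share misdated by 8 days | Expected ratio | Power at 29 cases | Cases for 80% |
|---|---|---|---|
| 0% | 24/8 = 3.00 | 80% | 29 |
| 10% | 22.4/9.6 = 2.33 | 58% | 47 |
| 20% | 20.8/11.2 = 1.86 | 36% | 85 |
| 30% | 19.2/12.8 = 1.50 | 18% | 194 |

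**If every case were misdated (f = 1):** L = 2 gives 20/12 = 1.67; L = 4 gives 16/16 = 1.00; L = 6 gives 12/20 = 0.60; L = 8 gives 8/24 = 0.33.

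**When the whole estimate falls below 1.** Setting the formula to 1 gives f = 16/(4L) = 4/L. The share must exceed 80% at L = 5, 67% at L = 6, 57% at L = 7 and 50% at L = 8. At L = 4 or less it never happens. Beyond 8 days the required share rises again: 57% at L = 10 and 80% at L = 14. From L = 16 on, even full misdating gives 1.00.

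**Longer or separated windows, all misdated.**
- SCRI 1-42 and 43-127, L = 8: risk (34×3 + 8)/42 = 2.62, control (8×3 + 77)/85 = 1.19, ratio 2.20. L = 20: 1.39.
- CCO 1-21 and 50-70, L = 8: (13×3 + 8)/21 = 2.24. L = 20: (3 + 20)/21 = 1.10.

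These counts keep cases whose event fell between dispensing and administration, because the first-code rule gives them an exposure date. If such cases were dropped instead, the fully misdated CCO ratio would be lower: 39/21 = 1.86 at 8 days, 1.00 at 14 and 0.14 at 20. The vaccinated case-coverage design was not quantified.

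**The case against.** The strongest reply is about reach. The source list is a menu for sites, joined by and/or; the protocol nowhere says that dispensing and administration records are merged for one person. A site with a single source discards no true date through this rule. Nothing in the document says how far dispensing precedes administration, or how often. The document is a template, the 21 days are an illustration, and investigators are told to write their own exposure definitions. All of this stands and limits the size of the problem. It does not remove it: the text states which code to keep, sites may hold both record types, and a template rule may be carried over unchanged.

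A reader might infer that the rule can reverse a real effect. Ratios such as 0.60 or 0.33 hold only if every case is misdated. Among the protocol's examples, with the rule applied as written, only the adjacent 0-7 and 8-15 pair reverses, and then only with a majority misdated. Section 9.2.5.3 also allows a washout: with control days 16-23 and a 6-day lag, full misdating gives 12/8 = 1.5, not 0.60. The SCRI is the primary analysis in only one of the four Table 2 scenarios.

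A reader might also infer that two records of dose 2, on days 28 and 30, would both be kept because each is at least 21 days after the first code. The example's wording allows that reading, but the general sentence it illustrates asks for sufficient spacing between code dates, and codes two days apart fail it. This is a matter of wording.

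**Conclusion.** The point holds as a one-directional dating error in a stated rule. It arises only where one person has both a dispensing and an administration record with different dates. Its usual effect is attenuation and lost power: for windows 0-7 and 8-15, a true ratio of 3 and an assumed 8-day lag, the expected ratio is 2.33 to 1.50 for 10% to 30% misdated, and power at Table 3's 29 cases drops from 80% to between 58% and 18%. With 1-42 and 43-127 or the CCO example, the same lag leaves about 2.2 even if everyone is misdated. The documents do not support a claim that the rule would reverse a site's or a pooled result, because they give no lag and no affected share.

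**What to change.** In section 9.2.5.2, replace the first-code rule with wording to this effect:

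*Codes closer together than the minimum spacing derived from the dosing schedule are one dose. The dose is dated by its recorded administration date (immunisation register, general practice or medical record, or vaccination card) in preference to a dispensing date. A dispensing date is used only if no administration date exists; it is flagged, and such cases are excluded in a sensitivity analysis. The same date rule applies to a single-dose vaccine.*

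Add that sensitivity analysis to section 9.6.5. The protocol gives no ground for ranking cards above other administration sources; section 9.2.5.2 treats cards as something to validate.

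As a wording alignment only, let the example count spacing from the last retained dose, in line with the general sentence before it.

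The cost is a source rank and a flag in the common programme, and one more sensitivity analysis. No new data are needed.

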9.2.5.3 Risk and Control Windows

In this section, risk/exposure windows will be defined for <<adverse event>> in table format.

SCRI

If the SCRI is used, a risk window, in which person-time will be considered exposed, will be selected after vaccination to reflect the hypothesised period of increased risk of the outcome due to vaccination. By convention, the risk window will index on the date of vaccination, which will be time = 0. A postvaccination control window will be selected to estimate the baseline rate of the outcomes. The control window definition (length and timing relative to vaccination) will be the same across individuals and will balance the need to obtain adequate statistical power against the threats of bias due to loss to follow-up and time-varying confounding. A washout period following the risk window may be incorporated to avoid any carryover effects of the vaccine into the postvaccination unexposed person-time.

If multiple doses of vaccine are given during the study period, the risk and control windows of one dose must not overlap with the risk or control windows of a subsequent dose, based on the vaccine dosing schedule. Some possible approaches to define the control interval, depending on the length of the risk interval and spacing between doses of the vaccine, are provided below:

- If there is a short interval between doses of the vaccine and a long risk interval, it would be necessary to avoid overlap of the risk interval of one dose with the risk and/or control intervals of a subsequent dose; depending on the length of the risk interval and the spacing between doses, it may be necessary for the control interval to be positioned after the risk interval of the final dose. For example, suppose the vaccine is administered in two doses approximately 28 days apart, and the outcome of interest has a risk interval of 1 to 42 days. Conducting a dose-level analysis (i.e., considering each dose to be a separate observation), with a risk interval of 1 to 42 days following each dose could potentially lead to confounding of the first dose by receipt of the second dose, and vice versa. To address this, a person-level analysis could be conducted combining the risk intervals following each exposure, for example:
 - For persons who receive two doses, define the risk interval as 1 to 42 days after the first dose plus 1 to 42 days after the second dose. The control interval could then be defined as 43 to 127 days after the second dose.
 - For persons who receive only one dose, define the risk and control intervals as 1 to 42 and 43 to 127 days after vaccination, respectively.
 - In the above scenarios, the control window could be placed even further in time from vaccination to incorporate a washout period between the risk and control intervals, as needed.
- If there is a short interval between doses of the vaccine but the risk interval is short, a dose-level analysis (treating each dose as a separate observation) could be conducted, but care must also be taken to ensure that the control interval does not overlap with the next dose. For example, suppose the vaccine is administered in two doses approximately 28 days apart, and the outcome of interest has a risk interval of 0 to 7 days. The control interval would need to end before 27 days after vaccination (e.g., 8-15 days) to ensure that there is no overlap of the control interval of the first dose with the risk interval of the second dose.

If the outcome affects the likelihood of a subsequent vaccination after the first dose, the impact of this potential bias could be explored in a sensitivity analysis using Farrington’s pseudolikelihood method for perturbed, censored, or curtailed observation periods for postevent exposures [7].

CCO Design

If the CCO design is used, an exposure window preceding the event will be selected to reflect the period during which exposure to COVID-19 vaccination is hypothesised to trigger the adverse event of interest. A single comparison window preceding the risk window will be selected to reflect the baseline prevalence of exposure; the comparison window should be selected independently of exposure status. Multiple comparison windows per case may also be considered but are not recommended because they may increase the potential for bias due to time-varying confounding and temporal trends in

exposure. By convention, the exposure window will index on the date of the adverse event, which will be time = 0. A washout period between the exposure and comparison windows can be implemented to avoid any carryover effects of the vaccine between the two windows.

If multiple doses are given during the study, the comparison window should be selected such that the underlying propensity to be vaccinated is not correlated between the exposure and comparison window. This guidance is given because individuals who are vaccinated in both windows do not contribute to the analysis and excluding a large number of individuals due to this reason reduces statistical power and precision of risk estimates. As an example, suppose the vaccine dosing schedule calls for two doses approximately 28 days apart, and the risk window is 1 to 21 days prior to the event. If one were to select a control window of 22 to 42 days, we anticipate that many persons would be vaccinated in both windows and become uninformative to the study. To avoid this, the comparison window could be defined as 50 to 70 days before the event; the comparison window could be placed even further before the event to incorporate a washout period between the exposure and comparison window, as needed.

